#### Rationale for estimand:

Discontinuation of study treatment due to AE, discontinuation of study treatment due to lack of efficacy and use of rescue medication will affect the early clinical response thus the early clinical response will be counted as failure under composite strategy.

The reasoning of treatment policy is to estimate the early clinical response until subjects are on study will be collected and reported (regardless of the intercurrent event occurring).

#### 2. Primary clinical response at end of therapy [EOT (Day 12 to 14)]

- Population:  
Children with acute respiratory tract infections (ARTIs) in India between 6 months to 12 years of either gender.
- Treatment conditions:  
Augmentin (ES)-600 with dose level 90/6.4 mg/kg/day twice daily (12 hourly) for 10 days.
- Variable/Endpoint:  
Proportion of successful primary clinical response at end of therapy (EOT) visit.
- Summary measure:  
Counts and percentages for primary clinical response at end of therapy (EOT) visit with corresponding 95%CI
- Intercurrent events (ICEs):
  - Lack of compliance (<80%) - Principal stratum  
Only those subjects who have at least ( $\geq$ ) 80% compliance would be considered in the calculation for proportion of primary clinical response
    - Discontinuation of study treatment due to AE, discontinuation of study treatment due to lack of efficacy and use of rescue medication - Composite strategy

If subject discontinue due to above mentioned three ICEs, then primary clinical response for that subject will be imputed as a failure.

- Discontinuation of study treatment due to any other reason – Treatment Policy

#### Rationale for estimand:

Lack of compliance (<80%) will impact on primary clinical response therefore subjects who have at least ( $\geq$ ) 80% would be considered for primary clinical response under principal stratum strategy.

Discontinuation of study treatment due to AE, discontinuation of study treatment due to lack of efficacy and use of rescue medication will affect the primary clinical response thus the primary clinical response will be counted as failure under composite strategy.

The reasoning of treatment policy is to estimate the primary clinical response until subjects are on study will be collected and reported (regardless of the intercurrent event occurring).

No intercurrent event is defined for secondary clinical response endpoint as no events are expected to occur during the follow-up period. The data will be analyzed as collected.

No intercurrent event is defined for Protocol-defined diarrhoea (PDD) endpoint. The data will be analyzed as collected.

### **3. STUDY DESIGN**

#### **3.1. GENERAL DESCRIPTION**

This study is an open label, multi-centre, non-comparative study. Subjects will be children aged between 6 months to 12 years, presenting with ARTIs including AOM, ABRS and CABP.

At Preliminary Visit (Day 0) after signing the inform consent form by the parent/guardian and assent form by children between 7 to 12 years of age, a series of screening evaluations will be performed in order to determine whether prospective study participant meets the inclusion criteria. Enrolled and screen passed subjects will receive Augmentin (ES)-600 at 90/6.4 mg/kg/day administered in two divided doses, every 12 hours with food for 10 days.

The incidence of protocol-defined diarrhoea will be determined from information collected from the Patient Diary cards, which will be appropriately translated for all languages required based on sites participating in the trial.

---

Document:	\leedc-vnasc01\BIOSdata\GSK\BRL25000	PPD	Biostatistics\Documentation\SAP
Author:	PPD	Version Number:	V1.0
		Version Date:	18JUL2022
Template No.: CS_TP_BS016 Revision 6		Reference: CS_WI_BS005	

Effective Date: 02Dec2019

After a minimum of two treatment days (four doses) of study intervention has been taken, an 'on-therapy' (OT) visit will be scheduled between Day 3 and 5. During this visit, the investigator/study coordinator shall assess safety (primary endpoint) and 'early clinical response' (secondary endpoint). Safety parameter includes treatment emergent adverse events (TEAEs) for primary study objective. Additionally, clinical status, study intervention compliance, completion of Patient Diary cards, and concomitant medications use will also be assessed. The Investigator will assess safety parameters and clinical status whereas study coordinator will check other parameters with coordinated effort.

Subjects with clinical 'failure' or having PDD or severe AE or SAE at OT visit (Day 3 to 5), will be withdrawn from the study intervention (as per Investigator discretion) and treated appropriately. In such case, the OT visit will be considered as End of Therapy (EOT), and all evaluations that are planned at scheduled EOT (Day 12 to 14) will be completed in this visit. However, these Subjects will return at FU visit (Day 22 to 28) for safety assessment.

Subjects with clinical 'failure' or having PDD or severe AE or SAE after OT visit (Day 3 to 5) but prior to EOT, will be scheduled to return to the site for an interim evaluation, within 24 hours of notification to the Investigator. Subjects will then be withdrawn from the study intervention (as per Investigator discretion) and treated appropriately. In such case, the interim visit will be considered as EOT visit, and all evaluations that are planned at scheduled EOT (Day 12 to 14) will be completed in this visit. However, these Subjects will return at FU visit (Day 22 to 28) for safety assessment.

The Subjects continuing in the study will return for the scheduled 'end of therapy' (EOT) evaluation between Day 12 and 14. The Investigator will enquire the participant or parent/legal guardian about development of AEs and use of concomitant medication(s).

The Investigator will perform safety (primary endpoint) and primary clinical response (secondary endpoint) evaluation. Patient Diary cards and unused medication will be returned at this visit.

[figure not shown]
Subjects who experience recurrence of signs/symptoms *after* EOT visit (Day 12 to 14), but prior to scheduled FU visit (Day 22 to 28) will be required to visit the study site twice post EOT - once for the interim visit at the time of any recurrence (Day 15 to 21) and for the scheduled FU visit (Day 22 to 28). At the interim visit, all the evaluations which are to be performed at scheduled FU visit will be conducted. However, in such cases, all evaluations except secondary clinical response will be repeated at scheduled FU visit (Day 22 to 28). All Subjects experiencing recurrence post EOT will be treated according to the Investigator's discretion.

All Subjects, including withdrawals or clinical ‘failures’ at EOT or had disease recurrence after EOT, will return for scheduled FU visit on Day 22 to 28. This visit is required for safety assessment and administration of additional medication, if warranted.

The Subjects continuing in the study will return for the scheduled 'follow-up' (FU) visit between Day 22 and 28. The visit be considered as 'end of study' visit, where the Investigator will perform final safety (primary endpoint) and secondary clinical response (secondary endpoint) evaluation (except for recurrence) during the visit.

In general, FU visit at Day 22 to 28 includes both safety and efficacy assessment for Subjects who were clinical ‘success’ at EOT, but only safety assessment for the Subjects who were clinical ‘failures’ at EOT or had disease recurrence after EOT. These Subjects are, by definition, clinical failures at follow-up visit.

Table 2: Study Flow Chart

### 3.2. SCHEDULE OF EVENTS

Schedule of events can be found in Section 1.3 of the protocol.

### 3.3. CHANGES TO ANALYSIS FROM PROTOCOL

There is no change in analysis from protocol.

## 4. PLANNED ANALYSES

### 4.1. DATA MONITORING COMMITTEE (DMC)

There will be no DMC for this study.

### 4.2. INTERIM ANALYSIS

There will be no Interim analysis for this study.

### 4.3. FINAL ANALYSIS

All analyses identified in this SAP will be performed by IQVIA Biostatistics following Sponsor Authorization of this Statistical Analysis Plan and Database Lock.

## 5. ANALYSIS POPULATIONS

The following analysis population will be defined for this study:

### 5.1. ENROLLED POPULATION [ENR]

The all subjects enrolled (ENR) population will contain all subjects who provide informed consent for this study.

This analysis population will be used to summarize subject disposition (screen failures and reason for screen failure).

### 5.2. INTENT TO TREAT POPULATION (ITT)

All Subjects who are enrolled and receive at least 1 administration of the investigational product (Augmentin [ES]-600) will be included in the intent-to treat population. The ITT population will be used for all safety and efficacy analyses.

---

Document:	\\ieedc-vnasc01\BIOSdata\GSK\BRL25000	PPD	Biostatistics\Documentation\SAP
Author:	PPD	Version Number:	V1.0

Template No.: CS\_TP\_BS016 Revision 6      Reference: CS\_WI\_BS005

Effective Date: 02Dec2019

## 6. GENERAL CONSIDERATIONS

### 6.1. REFERENCE START DATE AND STUDY DAY

Study Day will be calculated from the reference start date and will be used to show start/stop day of assessments and events.

Reference start date is defined as the day of the first dose of study medication, (Day 1 is the day of the first dose of study medication) and will appear in every listing where an assessment date or event date appears.

If the date of the event is on or after the reference date, then:

- Study Day = (date of event – reference date) + 1.

If the date of the event is prior to the reference date then:

- Study Day = (date of event – reference date).

In the situation where the event date is partial or missing, Study Day, and any corresponding durations will appear partial or missing in the listings.

### 6.2. BASELINE

The baseline values (non-missing) for each parameter will be the last available assessment result prior to the first dose of study administration. In case first dose can be given on Day 0 (after laboratory test result availability), the same will be considered as Day 1.

- Change from Baseline = Post-Dose Visit Value – Baseline
- Percentage Change from Baseline =  $100 \times [(Post-Dose Visit Value - Baseline) / Baseline]$

### 6.3. COMPUTATION OF AGE

Each subject's age will be calculated based on their date of birth relative to the date of the preliminary visit. Where only a subject's year of birth is collected, their date of birth will be imputed with 30th June (30 Jun YYYY).

---

Document:	\\ieedc-vnasc01\BIOSdata\GSK\BRL25000\PPD	Biostatistics\Documentation\SAP
Author:	PPD	Version Number: V1.0
		Version Date: 18JUL2022
Template No.:	CS_TP_BS016 Revision 6	
Effective Date:	02Dec2019	
		Reference: CS_WI_BS005

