5. STUDY POPULATION

5.1. Inclusion Criteria

Participants are eligible to be included in the study only if they meet all the below inclusion criteria:

1. Age: 6 months to 12 years of either gender.

2. **Diagnosis of AOM on basis of otoscopic findings as defined below:**

- Purulent otorrhea of less than 24 hours duration
- OR
- Middle ear effusion (MEE)
 - Middle ear effusion is evidenced by at least two of the following:
 - Decreased or absent tympanic mobility measured by pneumatic otoscopy,
 - Yellow or white discoloration of the tympanic membrane, or
 - Opacification of the tympanic membrane.

PLUS

At least one of the following indicators of acute inflammation:

- Ear pain within 24 hours, including unaccustomed tugging or rubbing of ear,
- Marked redness of the tympanic membrane, or
- Distinct fullness or bulging of the tympanic membrane.

OR

Child with ABRS with inflammation as bacterial infection who has the following symptoms/signs on the day of or the day before the first dose of the investigational product:

- Redness of the nasal mucosa
- Nasal or postnasal discharge is purulent or mucopurulent
- Pathological shadow in the paranasal sinus on a radiogram (only for reference-based on investigator discretion). Patient with surgical history should be excluded but patient with a previous surgery more than 365 days before and apparently preserved maxillary sinus mucosa or patient with a previous surgery of nasal polypectomy more than 90 days before may be enrolled in the study.

- Child with ABRS whose severity is classified as moderate or severe (total score ≥ 4) based on the nasal cavity findings and symptoms as shown below.

		None	Mild/small amount	Moderate or severe
Symptom	Rhinorrhoea	0	1	2
	Bad mood/ productive cough	0	1	2
Nasal cavity finding	Nasal/postnasal discharge	0 (Serous)	2 (Mucopurulent, small amount)	4 (Moderate or larger amount)

The severity of condition will be determined by the total score of the above symptoms/findings:

1 to 3 = mild, 4 to 6 = moderate, 7 to 8 = severe.

OR

Child diagnosed with CABP based on following criteria: (At least three of the four criteria should be met to include in the study)

- i. History of documented fever (rectal, ear, or oral temperature $\geq 38^{\circ}\text{C}$ or axillary temperature $\geq 37.5^{\circ}\text{C}$) or hypothermia (rectal, ear, or oral temperature $<35^{\circ}\text{C}$ or axillary temperature $<34.5^{\circ}\text{C}$)

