5.4.2. Screening, Enrolment and Baseline Assessments

Preliminary Visit (Day 0):

A series of screening evaluations will be performed at Preliminary Visit in order to determine whether prospective study participant meet the selection criteria for the study. The following assessments will take place at the Preliminary visit:

- The Investigator or designated study personnel will inform each participant's parent/ guardian of the nature of the study, explain the potential risks, and obtain written informed consent prior to performing any study-related procedures.
- Participant is 6 months to 12 years of age at the time of signing of informed consent by parent(s)/legal guardian(s), as applicable.
- Children between 7 to 12 years to assent prior to performing any study-related procedures.
- The participant and parent(s)/legal guardian(s) are willing and able to comply with the study protocol.
- In accordance with regional/local laws and regulations, the parent(s)/legal guardian(s) has given written informed, dated consent; and the participant (age 7 to 12 years) has given written assent, if applicable, to participate in the study.
- Assessment for eligibility against the inclusion and exclusion criteria.
- Medical history documentation.
- Demographic data (race, age, sex).

- Vital signs (body temperature, pulse rate, and respiratory rate).
- Physical examination (assessments of the skin, cardiovascular, respiratory, gastrointestinal, and neurological systems, height, and weight).
- Laboratory evaluations (hematology, plasma creatinine, aspartate aminotransferase [AST], alanine aminotransferase [ALT] and bilirubin).
- Chest X ray and X ray of nasal/paranasal sinus to be performed for patients presumed to have CABP and ABRS (only for reference, as per investigators discretion).
- Prior/concomitant medications.
- Baseline bowel movements.
- Documentation of the baseline signs and symptoms (other than disease under study).

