## 10. DEMOGRAPHIC AND OTHER BASELINE CHARACTERISTICS

The following demographic data and other baseline characteristics will be presented for the ITT population by overall and indication:

- Derived Age (years)
- Age in categories ( $\leq$  6 months,  $>$  6 months and  $<$  2 years,  $\geq$  2 years and  $<$  5 years,  $\geq$  5 years and  $<$  8 years,  $\geq$  8 years )
- Sex
- Race
- Ethnicity
- Weight (kg)
- Weight in categories ( $\leq$  12kg,  $>$  12 kg and  $\leq$  23 kg,  $>$  23 kg and  $\leq$  40 kg,  $>$  40kg )
- Height (cm)

Baseline characteristics will include vital signs parameters, bowel movements, and radiological assessments (X-Ray of chest and nasal/paranasal sinus), as performed at the time of preliminary visit.

Continuous demographic and baseline characteristics data will be summarized using descriptive statistics. For categorical data, counts and percentage of subjects in each category will be provided.

Subjects listing of demographic characteristics by indication will be provided for ITT population.

Document:	\\ieedc-vnasc01\BIOSdata\GSK\BRL25000	PPD	Biostatistics\Documentation\SAP
Author:	PPD	Version Number:	V1.0

Template No.: CS\_TP\_BS016 Revision 6

Version Date: 18JUL2022

Effective Date: 02Dec2019

Reference: CS\_WI\_BS005

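### For any child with only a year of birth on record, imputing 30 June misstates age by up to about six months, as much as the trial's minimum age, and distorts the infant age bands

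*SAP*

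**What the plan says.** SAP 6.3 states that each child's "age will be calculated based on their date of birth relative to the date of the preliminary visit". It adds a fallback: "Where only a subject's year of birth is collected", "their date of birth will be imputed with 30th June (30 Jun YYYY").

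SAP 10 lists "Derived Age (years") among the demographic items and bands age with cut-points at 6 months, 2, 5 and 8 years. The lowest band is 6 months or younger. These items are summarised overall and by indication, and demographic characteristics are listed by subject.

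Protocol 5.1 sets the age criterion as "Age: 6 months to 12 years of either gender". Protocol 5.4.2 applies it at consent ("Participant is 6 months to 12 years of age at the time of signing of informed consent") and names the items to be recorded at the preliminary visit: "Demographic data (race, age, sex"). Neither document says whether the eCRF holds a full date of birth or only a year, or whether age is recorded in months or in years. Neither sets a floor at 6 months, or prefers the recorded age, when the birth date is imputed.

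**The concern.** A mid-year birth date is a harmless convention in adults, where six months is a small fraction of age. Here the largest possible error equals the youngest eligible age, and the lowest reporting cut-point sits at that same age. With correct ages the lowest band should be almost empty, holding only children exactly at the minimum. Under the fallback it would take in older infants, most of them shown as younger than the protocol allows. Other children would cross the 2, 5 and 8 year cut-points in either direction.

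What is at stake is the description of who was exposed. The study exists to provide safety data in Indian children, and the age table tells a reader how much of that experience lies in infants. A reader who saw children of apparently 2 or 3 months could not tell that the imputation had produced them.

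**Working it through.** The SAP gives no figure for the size of this error, so there is none to reproduce. The check is date arithmetic.

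**Inputs.** Imputed birth date 30 June and reference date the preliminary visit (SAP 6.3); minimum age 6 months (Protocol 5.1); cut-points 6 months, 2, 5 and 8 years (SAP 10); 310 children (Protocol 9.2).

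**Step 1: error for one child.** Derived age minus true age = true birth date minus 30 June.
- Born 1 January: -180 days (-181 in a leap year), so age is understated.
- Born 31 December: +184 days, so age is overstated.
- Mean absolute error over the 365 birth dates: (0 + 1 + … + 180 + 1 + 2 + … + 184)/365 = (16,290 + 17,020)/365 = 91 days.

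**Step 2: children enrolled in their year of birth.** To be at least 6 months old, such a child must be born from 1 January to about 30 June and seen from 1 July to 31 December. True age is then 181 to 364 days (one day more in a leap year), but derived age is only 1 to 184 days. Listing every eligible pair of birth and visit dates in a non-leap year gives 16,710 pairs:
- counted in calendar months, derived age is at most 6 months on 183 of the 184 visit days, or 98.9% of pairs;
- counted as days/365.25, it is at most 0.5 year on 182 of the 184 days, or 97.8% of pairs;
- mean derived age is 123 days against a mean true age of 243 days;
- with the true birth date, only 1.1% of pairs (a child exactly 6 months old) belong in the lowest band.

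Example: a child born 5 January and seen 20 August is 227 days old (7.5 months) and is derived as 51 days (1.7 months).

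**Step 3: share of children in the wrong band.** Assumptions, none of them in the documents: every birth date is year-only, true ages are uniform from 0.5 to 12 (or 12.99) years, and enrolment is even over the calendar year. Let *a* be true age in years and *f* the position of the birthday in its year (0 to 1). Derived age is approximately *a* + *f* - 0.5.

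- Downward across 0.5 year: this needs *f* ≤ 1 - *a*, so the probability is 1 - *a* for *a* between 0.5 and 1. The area is ∫(1 - *a*) d*a* = 0.125. As a share of children aged 6 to 12 months this is 0.125/0.5 = 25%; day-by-day enumeration gives 24.4%.
- Upward across 2 years: by the same argument the area is 0.125. Under-2s in the wrong band: (0.125 + 0.125)/1.5 = 16.7%; simulation gives 16.5%.
- All children: 0.125 at 0.5 year, plus 0.25 (both directions) at each of 2, 5 and 8 years = 0.875. This is 0.875/11.5 = 7.6% with an upper age of 12.0 years, or 0.875/12.49 = 7.0% with 12.99.

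**Step 4: counts in 310 children.** Falsely at 6 months or younger: 310 × 0.125/12.49 = 3.1 to 310 × 0.125/11.5 = 3.4, so about 3. In any wrong band: 310 × 7.0% to 310 × 7.6%, or about 22 to 24.

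**The case against.** The strongest reply is that the fallback may never be used. The rule in SAP 6.3 is to calculate age from date of birth; 30 June enters only when the year alone is collected, and nothing in the documents shows that this applies to any child. If full dates are collected, the effect is nil. This stands, and every percentage in step 3 depends on it. A reader might infer that nearly all infants enrolled in their birth year will be reported as 6 months or younger. The documents support that only for children with year-only dates.

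The second reply is that even the worst case is small: about 3 of 310 children falsely in the lowest band. Errors run in both directions, so mean age over all children hardly moves (with birthdays spread evenly, the average error is 183 - 181 = +2 days). This also stands, although a sample weighted towards infants would raise the count and the documents give no expected age distribution.

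Third, a reader might infer that infants who look under-age would be logged as eligibility deviations. The documents do not support this. Age is checked at consent (Protocol 5.4.2), and important deviations are taken from CTMS logs and reviewed with the investigator or sponsor (SAP 9.2). No section derives a deviation from the imputed age. At most, an odd value might prompt a query.

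Fourth, no inferential output uses age. Protocol 9.4.1 rules out subgroup analysis, SAP 7.1 has no covariates, the ITT population is defined by enrolment and dosing, and doses and the overdose check go by weight (Protocol 6.2, SAP 14 and Appendix 4). This is correct and limits the point to descriptive reporting. It does not defend the rule: if no dates are year-only the sentence is unnecessary, and if some are it gives wrong ages for them.

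**Conclusion.** The point holds in conditional form. For any child with year-only birth data, SAP 6.3 produces an age wrong by up to about six months in a trial whose minimum age is 6 months. For such children enrolled in their calendar year of birth, 98% to 99% of possible date pairs give a derived age of 6 months or younger. These two results are exact date arithmetic.

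The shares for the whole sample (about 24% to 25% of children aged 6 to 12 months, about 17% of under-2s, 7% to 7.6% overall) are a worst case. They assume that all dates are year-only and that ages and enrolment are uniform; the true share of year-only dates is unknown and may be zero.

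Only the derived-age and age-band summaries and the demographic listing are affected. It would go too far to say that the TEAE, clinical response or diarrhoea results are compromised. This is a modest reporting fault, worth correcting because a better value is already among the data the protocol asks for.

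**What to change.** Replace the fallback sentence in SAP 6.3 with a rule of this kind: where the full date of birth is not available, age is the age recorded at the preliminary visit (Protocol 5.4.2), in completed months for children under 2 years; it is not derived from an imputed birth date. Note under the age table in SAP 10 that, for these children, the lowest band means 6 completed months, so it can include a child just short of 7 months. No eligible child would then appear below the inclusion limit, and the error would be under one month in children under 2 years.

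The cost is one SAP sentence and a footnote, plus one eCRF field if age is now recorded only in whole years.

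Collecting month and year of birth and imputing a mid-month day is an alternative, with a maximum error of about half a month. It is open only if it fits Protocol 10.1.4, which bars the transfer of identifying information to the sponsor. If year-only collection was chosen for that reason, the recorded age is the safer route. If the eCRF already captures full dates for every child, the fallback sentence can simply be deleted.
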